7.6 Post-intervention Follow-up Period – N/A

	Pre-Screen	Screen	Baseline	Week 1	Week 6	Week 12

7.7 Methods for Clinical Procedures – N/A

7.8 Study Parameter Table

Consent		X				
Flow Sheet			X		X	X
Screening Form (A) (To be completed on eligible and ineligible patients that do not want to participate)		X				
HADS-Anxiety/Depression Scale ^{64-66, 68-70} (pre-screen if done by phone in advance OR at baseline if done in person).	X (C)				X	X
Distress Thermometer (1 item)	X					
Modified Cancer Acceptance Scale (2 items)	X					
Cancer Worry Scale (8 items) ⁹⁵			X		X	X
Spirometry (FEV1)			X			X
Cancer Dyspnea Scale (CDS) ^{62, 63, 67, 73} Will be needed for registration			X (D)		X	X
PROMIS Fatigue ⁷⁹			X		X	X
Manchester Cough in Lung Cancer Scale ⁸⁰			X		X	X
Activities Form			X		X	X
Current Medications			X			X
Weekly Check-In Call/Data Capture from Device (via telephone interview)			X	Weekly (1-12)		
Participant Expectations ^{74, 75}			X			
Intervention Feedback						X
Early Withdrawal Form		If patient withdraws prior to completion of study.				
RNA/DNA Labs		X				X
Salivary cortisol collection (B)		X				X
** Visual Analogue Scales for Distress, Anxiety, and Dyspnea ^{71, 72}		
Should be requested by mail and submitted at Week 6 and at completion of the Week 12 study.
 
Completed before and after a single use of the device each week during Weeks 1-12.
 
(Participant will need several double sided forms) 1 selected use/week x 12 weeks = 12 forms
				

(A) Designated staff person at each site will log-in to CCRBIS to enter data in the screening log for all potential participants screened (necessary for the Primary Study Aim examining feasibility).

- (B) *Participants with endocrine disorders (e.g., diabetes and thyroid disorders) or on steroid-based medications are excluded from the salivary cortisol portion of the study. Topical steroid medications (creams/ointments) are permitted
- (C) Pre-screen HADS may be used for baseline and does not need to be repeated.
- (D) CDS will need to be collected prior to registration

7.9 Off Treatment Criteria

Participants may stop using the device for the following reasons: completed the protocol-prescribed intervention, adverse event or serious adverse event, inadequate device functioning, noncompliance, or medical contraindication.

Participants will continue to be followed, if possible, for safety reasons and in order to collect endpoint data according to the schedule of events. Participants will not be replaced for discontinuing the device.

7.10 Off Study Criteria

Participants may go “off-study” for the following reasons: the protocol intervention and any protocol-required follow-up period is completed, adverse event/serious adverse event, lost to follow-up, non-compliance, concomitant medication, medical contraindication, withdraw consent, or death.

We anticipate an approximate 20% attrition rate, and the total sample size has been adjusted accordingly.

8. PROTOCOL SPECIFIC TRAINING REQUIREMENTS

8.1 Specific Training Procedures or Certification Procedure

Several methods will be used in training sites. A training session will be held at the annual Research Base meeting and/or other meetings as designated by Drs. [name] and [name].

9. SPECIMEN MANAGEMENT

9.1 Blood for Research Testing

Blood samples will be shipped and stored with a unique identifier and will not include any information protected by HIPAA regulations. Storage for blood samples is located at Wake Forest University Baptist Medical Center.

Center for Genomics & Personalized Medicine Research
Wake Forest School of Medicine
[name]
[name]
[name]
[contact]

(See Appendix 18 and 19 for further lab instructions.)

After study-related tests have been performed, blood samples/blood derivatives (serum, plasma, PBMCs and their derivatives) are returned to the freezer. Samples will be stored for up to 60 days to allow assay data to be reviewed by the supervisor and samples needing to be

retested identified. Samples needing retesting are again thawed, analyzed and refrozen. After assays are complete, samples will be disposed of per applicable waste handling regulations.

10 REPORTABLE ADVERSE EVENTS/SERIOUS ADVERSE EVENTS

Only report **unexpected serious adverse events**, Grades 4 and 5, which are related to the use of the breathing device used in this study.

Adverse Event/Serious Adverse Event reporting begins after the informed consent is signed. Serious Adverse Events occurring within 30 days of study completion must be reported via FDA Form 3500 (MedWatch).

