The NCORP staff member will instruct each participant in use of the RESPeRATE device at baseline. Participants will be told that RESPeRATE analyzes a person's breathing pattern and plays 2 distinct tones that guide the person to inhale and exhale. The RESPeRATE control device looks and sounds identical but is not programmed to gradually slow breathing rate as in the active intervention arm. All participants will be provided with written instructions for the assigned device and will be observed using the device during the visit. To enhance adherence, we will have a NCORP staff member call participants weekly to assess experience with the device, troubleshoot difficulties that may have arisen and obtain breathing data for the prior 7 days. Participants who have not been using the device at the recommended frequency will troubleshoot ways of overcoming barriers to adherence as needed.

Self-reported dyspnea and spirometry (FEV1) include questionnaires and a pulmonary function test (PFT). These measures will be administered in-person at the NCORP site during baseline and post-intervention (Week 12) assessments. A shorter battery will be administered mid-intervention via mailed paper questionnaire with a stamped return envelope enclosed (Week 6). Any serious adverse event grade 4 or 5 related to the intervention will be reported to the WF NCORP RB at the time they become known to the NCORP site. (See Section 10.0)

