11.4 Data and Safety Monitoring Board

The Data Safety Monitoring Board meets every six months to review all phase II and phase III protocols. The Board includes members demonstrating experience and expertise in oncology, biological sciences and ethics. The DSMB report is generated by the statistician and includes a summary of accrual, adherence, and retention, descriptive statistics for baseline characteristics and patient status, descriptions of all adverse events and toxicities, estimates of data completeness, a summary of the primary and secondary outcome measures.

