12.7 Evaluation of Toxicity

All participants will be evaluable for serious adverse events from the time of their randomization. Toxicities will be evaluated using the NCI Common Terminology Criteria for Adverse Events (CTCAE) version 4.03. Fisher exact tests will be used to assess differences in toxicity rates between the three arms.

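### The safety-reporting rules in Sections 7.1, 10 and 12.7 disagree, and the plan names no source for the adverse-event data that the three-arm toxicity test and the DSMB report need

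*Combined protocol and SAP*

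**What the plan says.** **Reporting.** Section 7.1 states: "Any serious adverse event grade 4 or 5 related to the intervention will be reported to the WF NCORP RB", and refers the reader to Section 10. Section 10 tells sites to report only "unexpected serious adverse events", limited to "Grades 4 and 5, which are related to the use of the breathing device used in this study". Its next paragraph requires serious adverse events occurring within 30 days of study completion to go on the MedWatch form and repeats none of those limits.

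**Start of observation.** Section 10: "Adverse Event/Serious Adverse Event reporting begins after the informed consent is signed". Section 12.7: "All participants will be evaluable for serious adverse events from the time of their randomization".

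**Use of the data.** Section 12.7 grades toxicities by CTCAE 4.03 and adds: "Fisher exact tests will be used to assess differences in toxicity rates between the three arms". It sets no grade threshold, attribution rule or significance level. Section 11.4 says that the DSMB report includes "descriptions of all adverse events and toxicities", and Section 12.9 repeats this.

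**Collection.** Neither the form schedule in Section 11.1 nor the parameter table in Section 7.8 lists an adverse-event form. As described in Sections 7.1 and 7.3, the weekly call covers experience with the device, difficulties, adherence, breathing data and completion of the visual analogue scales. Flow Sheet/Addenda forms are due at Baseline, Week 6 and Week 12, and an Early Withdrawal Form exists. The text available does not show what either contains.

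**The concern.** There are two linked problems. First, a site cannot follow all the reporting passages at once. An expected, related grade 4 event is reportable under Section 7.1 but not under the opening rule of Section 10. An unrelated serious event shortly after completion falls outside both of those rules but inside the MedWatch sentence as worded.

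Second, the 7.1 rule and the opening rule of Section 10 both yield far less than Sections 11.4, 12.7 and 12.9 presuppose. Both filter on grade and relatedness before any analysis, and Section 10 also filters on expectedness. If those rules decide what reaches the database, the arm comparison rests on a few events already selected by site attribution, and the DSMB does not see all adverse events. The trial selects a dose for a later study on anxiety alone, so tolerability by dose is worth knowing.

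**Working it through.** **1. The passages side by side**

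| Place | Grade | Related only? | Unexpected only? | Start or window |
|---|---|---|---|---|
| 7.1 | 4-5 | Yes | No | When known to the site |
| 10, opening rule | 4-5 | Yes | Yes | From consent |
| 10, MedWatch sentence | Not stated | Not stated | Not stated | Within 30 days of study completion |
| 12.7, analysis | CTCAE, no threshold | Not stated | Not stated | From randomization |
| 11.4 and 12.9, DSMB | All | Not stated | Not stated | Six-monthly reviews |

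Section 7.1 and the opening rule of Section 10 differ only in expectedness. Aligning those two would therefore not supply the data for the last two rows.

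**2. The plan's own figures.** The plan gives no event rate, significance level or power for toxicity. Its sample size reproduces: 20 x 3 / 0.8 = 75, or 25 per arm. Simulating the selection rule with 20 per arm gives 0.901 for choosing the high dose with the required 0.5 SD margin and 0.900 for stopping under no effect. The plan states 90% for each. This point does not affect them.

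**3. What the three-arm Fisher test can show with 25 per arm.** A two-sided 0.05 level is assumed. With k affected participants in total, a split (a, b, c) has probability C(25,a) x C(25,b) x C(25,c) / C(75,k). The p-value sums this over all splits no more probable than the observed one.

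- k = 3, all in one arm: 3 x C(25,3) / C(75,3) = 3 x 2,300 / 67,525 = 0.102. This is the smallest p-value possible with three.
- k = 4, all in one arm: 3 x C(25,4) / C(75,4) = 3 x 12,650 / 1,215,450 = 0.031. A 3/1/0 split gives 0.315.
- k = 5, all in one arm: 0.009. A 4/1/0 split gives 0.119.
- k = 6, split 5/1/0: (3 x 177,100 + 6 x 1,328,250) / 201,359,550 = 0.042.

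Four affected participants are therefore the minimum. With four or five, all must be in one arm. With 20 per arm the pattern is the same (3/0/0 gives 0.100; 4/0/0 gives 0.030).

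**4. How likely four are, over assumed rates.** For a common rate p of reportable events, the expected number is 75p and the chance of none is (1-p)^75.

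| Assumed rate | Expected | P(none) | P(4 or more) |
|---|---|---|---|
| 0.5% | 0.4 | 69% | 0.06% |
| 1% | 0.75 | 47% | 0.7% |
| 2% | 1.5 | 22% | 6.4% |
| 5% | 3.75 | 2% | 52% |

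**5. Power under assumed unequal rates, by exact enumeration.** At 1/1/4% it is 1.1%, and at 0/0/10% it is 24%. For all-grade capture, a large excess (10/10/40%) gives 74%, but modest ones give little: 13% at 10/10/20% and 17% at 5/5/15%.

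**The case against.** Section 10 is headed as a rule on what is reportable, not on what is recorded. A narrow reporting rule beside wider toxicity data is ordinary practice, and Sections 11.4, 12.7 and 12.9 read as if wider data exist. The Flow Sheet or Early Withdrawal Form may hold them: Sections 7.9 and 7.10 list an adverse event as a reason for stopping the device or leaving the study, and Section 7.9 provides for follow-up on safety grounds. This stands. A reader might infer that the plan leaves almost no events to compare, or that non-serious effects are lost. The documents do not establish either, because those forms are not shown and no event rate is given. Nor is breathlessness unmeasured: the Cancer Dyspnea Scale is taken at Baseline, Week 6 and Week 12, and dyspnea is rated weekly before and after a session.

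A reader might also blame the extra expectedness filter in Section 10 for the scarcity. That is not supported, since Section 7.1 shares the grade and relatedness filters.

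The MedWatch sentence could be meant to inherit the limits above it, and a consent start for reporting can coexist with a randomization start for analysis. The text says neither.

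Finally, toxicity is not an endpoint or a criterion for going on to phase III, and low power comes partly from 25 per arm. Both are true. They limit the weight of the point but do not remove the contradiction or supply the missing data source.

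**Conclusion.** The contradiction stands on the text alone: Sections 7.1, 10 and 12.7 do not give one reporting rule or one start time. It also stands that the only adverse-event instruction to sites is narrower than the planned analysis and DSMB report, and that no described form or call is said to fill the gap.

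The consequence for the Fisher tests is conditional. If only reportable events are captured, no result with fewer than four affected participants can be significant, and at assumed rates of 0.5% to 2% four or more would occur in at most about 6% of such trials. A non-significant test would then carry no information on toxicity. The four-participant threshold needs only 25 per arm and the 0.05 level. Every probability and power figure rests on assumed rates. The feasibility aims, anxiety analysis and sample size are untouched. The change should be made, but the point does not undermine the trial's main purpose.

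**What to change.** 1. Reconcile Sections 7.1, 10 and 12.7 into one consistent reporting rule covering grade, relatedness, expectedness, the MedWatch window and the start time. State that it governs reporting only. Which rule applies is for the sponsor to decide.
2. In Section 12.7, name the data source and define the rate. For that analysis and the DSMB tables, use CTCAE events of any grade and attribution, recorded at the existing weekly calls and Week 12 visit. If the Flow Sheet already collects them, one sentence saying so is enough.
3. If only Section 10 events will be captured, replace the Fisher tests with a listing by arm and amend the DSMB wording in Sections 11.4 and 12.9 to match.

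The cost is a few sentences and, at most, one item on the weekly check-in form, with a small added burden for sites. All-grade capture would not make the comparison well powered at 25 per arm, so estimates by arm should be read with their uncertainty.

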11. STUDY MONITORING

11.1 Data Management Schedule

The Eligibility checklist/Registration Form should be completed on-line prior to placing the patient on study. Data forms will be submitted to the WF NCORP Research Base. See Section 6.4.1 for mailing address, or fax to [contact].

Form	Submission Schedule
HADS Form	Within 14 days of Pre-Screen or Baseline, Week 6, Week 12
Distress Thermometer	Within 14 days of Pre-Screen
Modified Cancer Acceptance Scale	Within 14 days of Pre-Screen
Cancer Worry Scale	Within 14 days of Baseline, Week 6, Week 12
Informed Consent	Within 14 days of Baseline
Cancer Dyspnea Scale (CDS)	Within 14 days of Baseline, Week 6, Week 12
Flow Sheet/Addenda	Within 14 days of Baseline, Week 6, Week 12
Current Medications	Within 14 days of Baseline, Week 12
Participant Expectations	Within 14 days of Baseline
PROMIS Fatigue	Within 14 days of Baseline, Week 6, Week 12
Manchester Cough in Lung Cancer Scale	Within 14 days of Baseline, Week 6, Week 12
Activities Form	Within 14 days of Baseline, Week 6, Week 12
Weekly Check-In/Call Data Capture from Device	Within 14 days of Week 6, Week 12
Visual Analog Scales	Within 14 days of Week 6, Week 12
RNA/DNA Lab Sample Form	Within 14 days of Baseline, Week 12
Intervention Feedback	Within 14 days of Week 12
Early Withdrawal Form	Within 14 days of Upon withdrawal from active treatment or consent
Screening Form (Eligible and Ineligible participants) **	Monthly

**** Designated staff person at each site will log-in to CCRBIS to enter data in the screening log for all potential participants screened (necessary for the Primary Study Aim examining feasibility).**

11.2 Case Report Forms

Participant data will be collected using protocol-specific case report forms (CRF).

11.3 Source Documents

Source documents are the original signed and dated records of participant information (e.g., the medical record, shadow chart) which may include electronic documents containing all the information related to a participant's protocol participation. Source documents are used to verify the integrity of the study data, to verify participant eligibility, and to verify that mandatory protocol procedures were followed. An investigator and other designated staff are required to prepare and maintain adequate and accurate documentation that records all observations and other data pertinent to the investigation for each individual participating in the study. All data recorded in the research record (including data recorded on CRFs) must originate in the participant's medical record, study record, or other official document sources.

Source documents substantiate CRF information. All participant case records (e.g., flow sheets, clinical records, physician notes, correspondence) must adhere to the following standards:

- Clearly labeled in accordance with HIPAA practices so that they can be associated with a particular participant or PID;
- Legibly written in ink;
- Signed and dated in a real time basis by health care practitioner evaluating or treating the participant; and
- Correction liquid or tape must not be used in source documents or on CRFs. Corrections are made by drawing a single line through the error. Do not obliterate the original entry. Insert the correct information, initial, and date the entry.

All laboratory reports, pathology reports, x-rays, imaging study and scans must have:

- Complete identifying information (name and address of the organization performing, analyzing, and/or reporting the results of the test); and
- Range of normal values for each result listed.

11.4 Data and Safety Monitoring Board

The Data Safety Monitoring Board meets every six months to review all phase II and phase III protocols. The Board includes members demonstrating experience and expertise in oncology, biological sciences and ethics. The DSMB report is generated by the statistician and includes a summary of accrual, adherence, and retention, descriptive statistics for baseline characteristics and patient status, descriptions of all adverse events and toxicities, estimates of data completeness, a summary of the primary and secondary outcome measures.

11.5 Record Retention

Clinical records for all participants, including CRFs, all source documentation (containing evidence to study eligibility, history and physical findings, laboratory data, results of consultations, etc.), as well as IRB records and other regulatory documentation will be retained by the Investigator in a secure storage facility in compliance with HIPAA, OHRP, FDA regulations and guidance, and NCI/DCP requirements unless the standard at the site is more stringent.

Record retention should be 5 years after the study is discontinued for studies without an IND (21 CFR 312.62).

11.6 CDUS Reporting

The Wake Forest NCORP Research Base Data Management Center will submit quarterly reports to DCP/CTEP by electronic means using the Clinical Data Update System (CDUS).

12. STATISTICAL CONSIDERATIONS

12.1 Study Design/Endpoints

Objectives: The objectives of this pilot study are:

- 1) To evaluate the feasibility of conducting a randomized phase III study to test the efficacy of device-guided breathing in post-treatment lung cancer survivors with significant anxiety. Feasibility will be assessed using measures of accrual, participation, adherence, and retention.
- 2) To collect preliminary data on the variability and efficacy of two doses of a device-guided breathing intervention versus a usual breathing control group for reducing anxiety (primary outcome) and for improving self-reported cancer-related worry dyspnea, and respiratory functioning (secondary outcomes) in post-treatment lung cancer survivors.
- 3) To select the optimal dose of the device-guided breathing intervention (15 minutes once/day or twice/day) for a subsequent randomized study. The optimal dose will be defined as the one that results in the greatest improvement in anxiety scores at 12 weeks.

A parallel, randomized pilot study will be conducted to address these objectives. Eligible patients will be stratified initial dyspnea level and randomized with equal probability to high dose device-guided breathing, low-dose device-guided breathing, or a usual breathing control. Study endpoints include anxiety (primary outcome: anxiety subscale of the HADS-Anxiety/Depression Scale), dyspnea, and respiratory function. These constructs will be measured at baseline and 6 and 12 weeks post-randomization. Estimates of treatment efficacy will be obtained using the "intent to treat" approach. That is, all randomized patients will be included in the primary analyses whether or not they were treated according to protocol.

- 4) Supplemental Objective: To determine if changes in anxiety attributed to device-guided breathing are correlated with epigenetic (DNA methylation) and/or gene expression changes.
- 5) Supplemental Objective: To obtain preliminary data on changes in salivary cortisol (diurnal slope, cortisol awakening response, area under the curve) in each intervention group and associations between salivary cortisol and anxiety.

12.2 Sample Size/Accrual Rate

The sample size for this trial will be based on statistical selection theory criterion as described by Simon et al.⁷⁷ For a selection trial, one simply chooses the regimen that results in the "best" response. While Simon used this idea in the context of choosing the regimen with the best tumor response, the idea is applicable to outcomes with other distributions (in addition to the binomial). In our trial, the response is self-reported anxiety, which we will assume is normally distributed, so the best regimen will be the one with the lowest mean anxiety score. We will proceed to a phase III trial if one of the RESPeRATE intervention arms results in the least anxiety, and the mean anxiety score in that group is at least 0.5 standard deviations (SD) less than mean anxiety score in the control group. The sample size is chosen to ensure a high probability of selecting the best arm, assuming that the mean anxiety score in the low dose arm is 0.5 SD less than the mean in the control group and the mean anxiety score in the high dose arm is 1.0 SD less than the mean in the control arm. Under these assumptions, we used

simulations to determine the sample size needed in each group to ensure that the probability of selecting the best regimen was 90%. We randomly selected n independent observations from the normal distribution with an SD = 1, calculated the mean anxiety scores for each group, and selected the group with the least observed mean. This was repeated 200,000 times. The probability that the best regimen was chosen is calculated as the proportion of times (of the 200,000 repetitions) that the group with the true lowest mean was selected. In addition to selecting the best regimen, we will only pursue a subsequent phase III trial if there is some evidence of effect. Thus, we will require that the mean in the best regimen is at least 0.5 SD lower than the mean for the control group. Using simulations, we find that 20 patients per group provides 90% probability that the best regimen will be chosen and the mean in that group be at least 0.5 SD lower than the mean in the control arm. Assuming a 20% dropout, we will accrue a total of 75 participants to this study (20x3/.8). Assuming no effect of the RESPeRATE device, we have 90% probability of stopping with the phase II trial.

